6.2.2 Clinical Laboratory Evaluations

*Screening laboratory tests will include:

- **Hematology:** hemoglobin, hematocrit, white blood cells (WBC) with differential count, platelet count. [DISCRETIONARY, may be ordered if physical exam or medical history indicates need.]
- **Biochemistry:** creatinine, total bilirubin, alanine aminotransferase (ALT), aspartate aminotransferase (AST), thyroid stimulating hormone (TSH). [DISCRETIONARY, may be ordered if physical exam or medical history indicated need.]
- **Urinalysis:** dipstick urinalysis, including protein, hemoglobin and glucose; toxicology and (when applicable) pregnancy testing.

6.2.3 Experimental Phase

Duration: 4 visits over 4-8 weeks

Timing: No more than 2 weeks between each visit.

While the provision of study treatment requires clinic attendance, we may conduct other components of the experimental visits remotely.

At each of the four visits, study staff will:

- *Record vital signs;
- Administer
MADRS,
CGI-I (except Visit 1 as this will be considered a baseline rating),
CGI-S,
C-SSRS, and
- MRI Safety Checklist; Record concomitant medications/therapies;
- *Administer the t-PBM session during MR Scanning;
- Record adverse events as reported by participant or observed by investigator.

In addition, participants will complete:

- PANAS,
- PBQ
- PCQ
- SDQ,
- ASQ,
- SAFTEE

- Neuro-QoL
- Q-LES-Q-SF, and
- TSRQ

MGH Site Neuronavigation: The BrainSight Neuronavigation System will be used at the MGH site to track the initial placement of the laser device on the subject's forehead and will be utilized to ensure accurate replication of positioning at each experimental visit. This is a recording device that does not involve any added risk or stimulation. Traditionally, this device is used to record precise location of EEG electrodes and transcranial magnetic stimulation (TMS) coils. In our case, we will be using it to record the position of the outlet of the laser before every PBM session. The BrainSight Neuronavigation System is FDA approved and is used as indicated. This device bounces light off of trackers that are placed on the forehead. Study staff lightly place a wand at various spots on the head. The system correlates the position of the wand with that of the trackers to precisely record the location of the head in relation to the photobiomodulation stimulation device. This is useful for later analysis, in which we will co-register the recorded laser position to the subject's MRI.

- For the NKI/NYU scans, lipid capsules are affixed to the device for demarcation of device location in the scans.

MR: Scanning will begin with acquisition of structural images and (for most subjects) a baseline MR thermometry scan. Subsequently we will collect approximately 60 minutes of functional data collection including ~20 minutes before t-PBM, ~20 minutes coinciding with t-PBM, and ~20 minutes following t-PBM, as well as (for most subjects) a post-t-PBM MR thermometry scan. (For technical and logistical reasons, we may opt to skip the thermometry scan for some subjects.)

Note that every scan performed in this study is saved and handled under the standard PHI confidentiality restrictions and regulations employed for patients' information. At least one scan per subject is additionally reviewed by a radiologist or neurologist with experience reading MRI scans, who might then detect an abnormality. If clinically useful information is uncovered, either the Principal Investigator or another clinician on the study will speak to the subject in person or on the telephone regarding the new information. A copy of the original image report will also be provided to the subject in person and the subject will be encouraged to follow up on the discovery with his or her treating physician.

t-PBM sessions: Across the four visits participants experience one session each of: 1) sham t-PBM; 2) low-irradiance t-PBM; 3) middle-irradiance t-PBM; and 4) high-irradiance t-PBM. The sequence in which the particular t-PBM parameters (summarized in Table 1) are utilized will be random.

6.2.4 Follow-up Phase

Duration: 1 phone call

Timing: Within one week of fourth t-PBM/scan session

Over the telephone study staff will administer the

- CGI-I
- CGI-S
- MADRS, and
- C-SSRS, and
- record concomitant medications/therapies and any adverse events.

Participants will also complete the following self-report scales remotely using Acquire:

- PANAS
- PCQ
- SDQ,
- ASQ,
- SAFTEE,
- Neuro-QoL

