- **The Perceptions of Blinding Questionnaire (PBQ) –The Perceptions of Blinding Questionnaire (PBQ)** – The PBQ is a self-report questionnaire to determine the degree to which the participant believes s/he is receiving the treatment or the sham.
- **Positive and Negative Affect Schedule (PANAS)⁴⁶** –This 20 item scale measures positive affect (e.g., excited, inspired) and negative affect (e.g., upset, afraid). Each item is rated on a five-point Likert Scale, ranging from 1 = *Very Slightly or Not at all*, to 5 = *Extremely*.
- **Montgomery-Åsberg Depression Rating Scale (MADRS)⁴⁷** –This 10-item clinician-rated instrument measures depression severity. It will be administered with a structured interview guide. The time frame for this scale is the past 7 days
- **Symptoms of Depression Questionnaire (SDQ)⁴⁸** – This is a comprehensive measure of depression that includes the assessment of symptoms in the anxiety–depression spectrum. It assesses irritability, anger attacks, and anxiety symptoms together with the commonly considered symptoms of depression. Analysis of the factor structure of the SDQ identified 5 subscales, including one in the anxiety–depression spectrum, with adequate internal consistency and concurrent validity.
- **Anxiety Symptoms Questionnaire (ASQ)⁴⁹** – This, is a 17-item self-report questionnaire measuring the frequency and intensity of 17 symptoms of anxiety, including nervousness, worrying, irritability, trouble relaxing, insomnia, lack of energy, difficulty concentrating, somatic symptoms, and impairment in functioning due to anxiety.
- **Adverse Events Form**- The Adverse Events Form captures any adverse event (serious or otherwise) specifically related to the application of the t-PBM.
- **Concomitant medications and therapies form** – This form records all ongoing medications, as well as other therapies targeting depression, and will be completed at every study visit, including the screening visit, as a safety-monitoring tool.
- **Quality of Life in Neurological Disorders, Cognitive Section (Neuro-QoL)⁵⁰** - The cognitive section of the Neuro-QoL is an 8 item self-rated measure of both executive function and general concerns. It measures perceived difficulties in cognitive abilities (e.g., memory, attention, and decision making) or in the application of such abilities to everyday tasks (e.g., planning, organizing, calculating, remembering, and learning).

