3.5.2 Secondary Study Endpoints

The secondary endpoints will be t-PBM effects on brain temperature, suicidal ideation/behavior, and the frequency and severity of adverse events and side effects occurring at the time of each t-PBM session and between each t-PBM session and the subsequent study visit. Brain temperature will be assessed with MR; suicidal ideation/behavior with the C-SSRS. Adverse events will be tracked with the adverse events log; side effects, with the SAFTEE and TSRQ.

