3.5.3 Exploratory Endpoints

The exploratory end points include the total scores of the following scales as assessed at the study visit subsequent to each t-PBM session: MADRS, SDQ, ASQ, Q-LES-Q-SF, and NeuroQoL.

4 Study Enrollment and Withdrawal

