4.4 Duration of Study Participation

Study participation should last between six and twelve weeks. Participants are required to attend one remote screen visit and five clinic visits (second screening visit and four scanning/t-PBM sessions) and answer questions during a single follow-up phone call. If scheduled for consecutive weeks, participants will complete the study in six weeks. However, for logistical regions the time between screening completion and the first scanning/t-PBM session can be as long as four weeks; in addition, as long as two weeks may pass between each scanning/t-PMB session.

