7.3 Time Period and Frequency for Event Assessment and Follow-Up

The occurrence of an AE or SAE may come to the attention of study personnel during study visits and interviews of a study participant presenting for medical care, or upon review by a study monitor. All AEs including local and systemic reactions not meeting the criteria for SAEs will be captured on the appropriate RF. Information to be collected includes event description, time of onset, clinician's assessment of severity, relationship to study product (assessed only by those with the training and authority to make a diagnosis), and time of resolution/stabilization of the event. All AEs occurring while on

study must be documented appropriately regardless of relationship. All AEs will be followed to adequate resolution.

Any medical condition that is present at the time that the participant is screened will be considered as baseline and not reported as an AE. However, if the study participant's condition deteriorates at any time during the study, it will be recorded as an AE. UPs will be recorded in the data collection system throughout the study.

Changes in the severity of an AE will be documented to allow an assessment of the duration of the event at each level of severity to be performed. AEs characterized as intermittent require documentation of onset and duration of each episode.

The PI will record all reportable events with start dates occurring any time after informed consent is obtained until 7 (for non-serious AEs) or 30 days (for SAEs) after the last day of study participation. At each study visit, the investigator will inquire about the occurrence of AE/SAEs since the last visit. Events will be followed for outcome information until resolution or stabilization.

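### The follow-up call after session 4 has no earliest day, so any call before day 7 makes the fourth dose's MADRS partly rate days before that dose

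*Combined protocol and SAP*

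**What the plan says.** - **Which contact rates which dose.** Section 3.5.3 takes the exploratory scales, MADRS among them, "as assessed at the study visit subsequent to each t-PBM session", and 9.3.5 repeats this. Section 3.5.2 counts adverse events and side effects at each session and "between each t-PBM session and the subsequent study visit".
- **Doses 1-3.** The next contact is the next session. Section 4.1 describes the sessions as weekly. Section 6.2.3 says "Timing: No more than 2 weeks between each visit", and 4.4 says "as long as two weeks may pass between each scanning/t-PMB session".
- **Dose 4.** The next contact is the telephone follow-up in 6.2.4, which includes MADRS, SAFTEE and the adverse-event record. Its rule is "Timing: Within one week of fourth t-PBM/scan session".
- **Recall.** For MADRS, section 2.1.8 states: "The time frame for this scale is the past 7 days". It gives no recall period for SDQ, ASQ, Neuro-QoL or Q-LES-Q.
- **Events after the end of participation.** Section 7.3 keeps recording open "until 7 (for non-serious AEs) or 30 days (for SAEs) after the last day of study participation".
- **Analysis.** Sections 9.3.3 and 9.3.5 model each outcome on dose (four categories), with order as a continuous variable and its interactions with dose. Order is dropped if no interaction appears; if one does, effect sizes come from first-week data only. Neither section has a term for days since dose.

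**The concern.** The rule for the call is an upper limit only, so a call on day 1, 2 or 3 complies. MADRS then asks largely about days before the fourth dose, yet the score enters 9.3.5 as that dose's outcome. With weekly sessions, those days are the third dose's follow-up period, so one dose's period is partly credited to another.

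The same early call leaves the fourth dose fewer days of SAFTEE coverage and active adverse-event enquiry than doses 1-3 receive. Event frequency depends on how long one looks, and 9.3.3 makes no allowance for that.

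At stake are the exploratory comparison of doses on depression severity and the between-session part of the secondary safety comparison. A shift confined to position 4 is also poorly described by a linear order term. If the short window blunts active-sham differences only at position 4, that is itself a dose-by-order interaction. Should it be detected, the plan's rule would restrict estimation to first-week data because of a measurement artefact.

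**Working it through.** **The plan's own figure.** The plan gives no figure for this point. The precision in 9.4 reproduces with n = 30 × 0.80 = 24 per dose: 1.2816 × √(2/24) = 0.370 (80% CI) and 1.960 × √(2/24) = 0.566 (95% CI), against the stated 0.37 and 0.57. Nothing below depends on it.

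**Inputs.** MADRS recall is 7 days (2.1.8). The call falls on day d after session 4, with d at most 7 (6.2.4). Sessions are nominally 7 days apart and at most 14 (4.1, 4.4, 6.2.3). Eight sequences come from two 4×4 Latin squares (9.5.1).

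**Step 1: share of the MADRS window before dose 4.** Share = (7 − d)/7.

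| Call day | Pre-dose days | Share |
|---|---|---|
| 1 | 6 | 86% |
| 2 | 5 | 71% |
| 3 | 4 | 57% |
| 4 | 3 | 43% |
| 5 | 2 | 29% |
| 6 | 1 | 14% |
| 7 | 0 | 0% |

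The latest permitted day is the only one without overlap.

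**Step 2: the same check for doses 1-3.** A 7-day gap covers post-dose days 0 to 7, with no overlap. A 14-day gap covers days 7 to 14, again with no overlap. A gap under 7 days would overlap; no minimum is stated, but the nominal spacing is weekly.

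**Step 3: weight of position 4.** In a 4×4 Latin square each dose is fourth once, so across two squares it is fourth in 2 of 8 sequences, or 1/4. With 24 completers that is about 6 per dose. Balance is approximate, because 15 treated per site (Table 2) is not a multiple of 8.

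**Step 4: dilution of a dose-sham contrast on MADRS.** Assume effect is proportional to post-dose days in the window, pre-dose days carry no effect, and doses 1-3 have no overlap. Dilution = 1/4 × (7 − d)/7.

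- All calls on day 7: 1/4 × 0 = 0%.
- All calls on day 3: 1/4 × 4/7 = 14%.
- All calls on day 1: 1/4 × 6/7 = 21%.

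**Step 5: scheduled event enquiry.** A call on day d gives dose 4 d days of SAFTEE and active enquiry, at most 7. Doses 1-3 get the gap to the next session, nominally 7 and at most 14 days. The documents say nothing about when calls will actually fall, so no average is calculated.

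**The case against.** The strongest reply is that the plan already intends a call about a week after session 4. Section 4.4 lists one remote screen, five clinic visits and one call. Those seven contacts at weekly spacing make six intervals, which matches the stated six weeks. A day-7 call complies and removes the overlap. This stands as a reading of intent, but 6.2.4 does not require it.

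Three stronger readings are tempting, and the documents do not support them.

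- *A reader might infer that one dose is favoured.* The Latin squares place every dose, sham included, fourth about equally often, so each has roughly the same mix of windows. What remains is dilution and a position effect.
- *A reader might infer that adverse-event observation for the fourth dose ends at the call.* Section 7.3 keeps recording open for 7 or 30 days after participation, and has the investigator ask participants at the last scheduled visit to report later events they think related. That follow-up is passive, but it is planned. Only SAFTEE and active enquiry stop at the call.
- *A reader might extend the overlap to anxiety and quality of life.* A 7-day recall is documented only for MADRS.

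The objection that the stakes are modest also stands. MADRS is exploratory, 9.1 puts estimation ahead of testing, and the BOLD endpoint and brain temperature are measured within the session.

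**Conclusion.** The gap is real and limited. Any compliant call before day 7 puts pre-dose days into the fourth dose's MADRS and shortens its scheduled side-effect enquiry, and no term in 9.3.3 or 9.3.5 corrects for this.

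The calendar shares (6/7 on day 1, 4/7 on day 3, 0 on day 7) follow directly from the text. The dilution of 0% to about 21% is an illustration. It rests on effect being proportional to post-dose days, on pre-dose days carrying no effect, and on weekly or longer spacing earlier. If the third dose still acts in those days the figure changes, and the documents give no basis for sizing that. A single average would need a distribution of call days, which the plan does not supply.

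The consequence is weaker contrasts on an exploratory outcome and on between-session side effects, plus a position-4 artefact. The primary endpoint and the go/no-go rule are untouched.

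**What to change.** 1. In 6.2.4, schedule the call, with its MADRS, SAFTEE and other remote scales, on day 7 after session 4. This stays within the one-week limit, so the C-SSRS and adverse-event contact is no later than now allowed. A window running to day 14 would delay that contact and is not needed.
2. Record days since the preceding session for every between-session outcome, including those after doses 1-3, whose gaps can run to 14 days.
3. In 9.3.3 and 9.3.5, add days since dose to the models, or an exposure-time offset for event counts. A covariate removes a shift in level but does not restore a diluted contrast, so this supplements the scheduling change.
4. Add a sensitivity analysis limited to MADRS ratings taken at least 7 days after the dose.

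The cost is slightly less flexibility in scheduling the call, one recorded interval per contact and a short analysis note. No contact is added. Windows will still differ between a 7-day and a 14-day gap after doses 1-3; items 2 and 3 make that visible and allow for it.

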6.2.5 Q-LES-Q-SF. Withdrawal/Early Termination Visit

If early withdrawal or termination occurs, every effort will be made to schedule and conduct all assessments initially scheduled for the **Follow-up Study Visit** (See **Section 6.2.4**).

6.2.6 Unscheduled Visit

Any unscheduled visits will be documented with notes to file to be kept in study subjects' binders.

6.3 Concomitant Medications, Treatments, and Procedures

All concomitant medications taken, and any other therapies intended to treat MDD that transpire, during study participation will be recorded on the case report forms (CRFs). For this protocol, a prescription medication is defined as a medication that can be prescribed only by a properly authorized/licensed clinician. Medications to be reported in the CRF are concomitant prescription medications, over-the-counter medications and non-prescription medications.

6.4 Prohibited Medications, Treatments, and Procedures

SSRIs, SNRIs, or psychotherapy are permitted but will need to be stable for at least 8 weeks prior to the screen. Any device-based interventions for depression will need to be discontinued, at least 8 weeks prior to screen. *Rationale: Other treatments initiated or modified close to the study intervention could potentially confound the effect of t-PBM on BOLD-MR signal.*

If, due to worsening depression or other medical event, a change in antidepressant therapies is required during the study, participants may be asked to withdraw at that time at the discretion of the principal investigators.

6.5 Prophylactic Medications, Treatments, and Procedures

N/A

6.6 Rescue Medications, Treatments, and Procedures

N/A

6.7 Participant Access to Study Agent at Study Closure

Participants will not have access to the study agent at study closure.

7 Assessment of Safety

7.1 Specification of Safety Parameters

In addition to recording and classifying adverse events (Sections 7.1 and 7.2), participants will also complete the SAFTEE and TSRQ at each visit.

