- **Quality of Life, Enjoyment, and Satisfaction Questionnaire (Q-LES-Q)¹¹¹**- Assesses subjective quality of life (i.e. physical health, subjective feelings, leisure activities and social relationships).
- **MRI Safety Checklist**- Identifies risk factors that may make MRI participation unsafe.
- **The t-PBM Self-Report Questionnaire (TSRQ)** – An open-ended questionnaire focusing on potential inconveniences and discomforts from the t-PBM.

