9.3.3 Analysis of the Secondary Endpoint(s)

For each subject at each t-PBM dose (including sham) we will compute changes in brain temperature using data recorded just before and after the t-PBM administration with MR thermometry scans.(Note that for technical and logistical reasons, some subjects may not undergo MR thermometry.) We will quantify the frequency and severity of suicidal ideation experienced as well as the presence or absence of suicidal behaviors after each t-PBM session using the C-SSRS. Finally, we will use the SAFTEE, TSRQ, and adverse events logs to determine the frequency and severity of side effects and adverse events. We will model these measures as a function of dose (considered a categorical variable with 4 levels) using mixed effects models¹¹⁷, including random subject intercepts to account for the potentially correlated measures on the same subject. Since the doses will be presented to subjects in a random order, the initial models will also include order of the dose (a continuous variable) and all interactions between the dose and the order. If there is evidence for an interaction effect between dose and order, this effect will be investigated to understand how the dose effect varies as a function of week of treatment, and in such case effect size of the t-PBM doses will be estimated using only the data when the dose was given in the first week. Whenever we find there is no interaction between dose and order, the order variable and the interactions will be omitted. The resulting models will be used to estimate the mean of each measure at each dose and the differences between each active t-PBM dose and sham.

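### No TSRQ is scheduled after a participant's last session, although 7.1 asks for it at every visit and 3.5.2 needs it up to the next one

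*Combined protocol and SAP*

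**What the plan says.** Section 3.5.2 makes side effects a secondary endpoint. It sets two windows, with events "occurring at the time of each t-PBM session and between each t-PBM session and the subsequent study visit", and assigns the measurement of "side effects, with the SAFTEE and TSRQ". Section 9.3.3 carries this into the analysis: "we will use the SAFTEE, TSRQ, and adverse events logs to determine the frequency and severity of side effects and adverse events", modelled by dose against sham. Section 7.1 gives the collection rule: "participants will also complete the SAFTEE and TSRQ at each visit". In the list of scales in section 2.1, the TSRQ is described as "An open-ended questionnaire focusing on potential inconveniences and discomforts from the t-PBM".

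Section 6.2.3 lists the TSRQ among the scales that participants complete at the four experimental visits. It does not say whether the form is completed before or after the scan.

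Section 6.2.4 covers the follow-up contact, within a week of the fourth session. It states that "Participants will also complete the following self-report scales remotely using Acquire" and lists the PANAS, PCQ, SDQ, ASQ, SAFTEE, Neuro-QoL and Q-LES-Q-SF. Staff also record adverse events. The TSRQ is not listed. For early withdrawal, 6.2.5 says that "every effort will be made to schedule and conduct all assessments initially scheduled for the" follow-up visit. Section 18 agrees with the text: the SAFTEE and the adverse-event form are marked under both Experimental and Follow-up, the TSRQ under Experimental only.

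**The concern.** The endpoint definition and the visit schedule do not match. For a dose given in session 1, 2 or 3 to someone who returns, the next experimental visit carries a TSRQ that can pick up what happened after the participant went home. For the last dose received, whether session 4 or the session before a withdrawal, no later TSRQ is scheduled.

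This matters because the secondary objective is to compare tolerability between doses, and some effects named in the protocol appear after the visit. Section 2.6.1 lists insomnia and irritability from the team's own research, and a same-day form cannot record a bad night that follows. If participants tended to leave after one particular dose, that dose would have thinner TSRQ coverage of its post-session window than the others.

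**Working it through.** **Instruments by contact** (sections 6.2.3 to 6.2.5 and Section 18)

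| Contact | SAFTEE | TSRQ | Adverse events |
|---|---|---|---|
| Screening | no | no | no |
| Four experimental visits | yes | yes | yes |
| Follow-up | yes | no | yes |
| Early termination (copies follow-up) | yes | no | yes |

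The omission appears independently in the visit text and in the schedule table. The broken heading at 6.2.5, which displaced only the Q-LES-Q-SF, does not explain it.

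**Inputs.** 30 participants with 4 sessions each (3.4); dropout of at most 20% (9.4). The timing of dropout is not given, so it is an assumption below.

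**The plan's own figure.** 30 × (1 − 0.20) = 24 per dose, which matches 9.4.

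**Windows with no later TSRQ, full completion.** Total windows: 30 × 4 = 120. Each participant has one last window: 30. Share: 30/120 = 25%.

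**With six dropouts, all after k sessions.** Windows: 24 × 4 + 6k. Last windows: 24 + 6 = 30.

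- k = 1: 30/102 = 29.4%
- k = 2: 30/108 = 27.8%
- k = 3: 30/114 = 26.3%

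**Spread over doses.** With full completion and doses balanced over positions, each dose is last in 30/4 = 7.5 participants on average, so the gap is even.

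The most uneven case is a deliberate extreme: all six dropouts leave after the same dose, given in position k (1, 2 or 3).

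- That dose: 30 delivered, with a later TSRQ in 30 − 7.5 − 6 = 16.5 (55%).
- Each other dose among the 24 completers: it is last in (24 − 7.5)/3 = 5.5, so a later TSRQ exists in 24 − 5.5 = 18.5. The dropouts add 6(k − 1)/3 = 0, 2 or 4 earlier sessions per dose, all followed by another visit. That gives 18.5 of 24, 20.5 of 26 or 22.5 of 28 (77% to 80%).
- Check: uncovered windows are 13.5 + 3 × 5.5 = 30, as above.

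**Dependence on when the form is completed.** If the TSRQ follows the scan, every delivered session has a same-day record and the gap is confined to later effects. If it precedes the scan, the last session has no TSRQ record at all. The documents do not settle which applies.

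**The case against.** The strongest reply is that the endpoint is already covered. Section 3.5.2 names the SAFTEE and TSRQ jointly and does not require each to span both windows. The SAFTEE is a systematic side-effect inventory and is in the follow-up and early-termination batteries. The Adverse Events Form is itself described in 2.1.8 as aimed at events related to t-PBM, and it is also in the follow-up column. Section 7.1.1 defines an adverse event broadly enough to include delayed discomfort, and 7.3 records non-serious events until 7 days after participation ends. This stands: a reader might infer that the side effects of the last dose go unrecorded, and the documents do not support that.

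The schedule can also be read as treating the TSRQ as a session-linked form, like the PBQ, which is likewise marked for experimental visits only. Completion before the scan would put the first TSRQ ahead of any exposure, so completion after it is the more natural reading. Heat or discomfort during irradiation would then be recorded even for someone who never returns. This is plausible, but it is not stated, and it does not fit the wording of 7.1 or the between-session window in 3.5.2.

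A reader might also infer that the gap biases the comparison in favour of a dose that drives people out. That would need effects that arise only after the visit and are reported neither on the SAFTEE nor as adverse events, together with withdrawals concentrated after one dose. Section 9.5.1 expects equal attrition across doses, and nothing in the documents makes that chain likely.

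Finally, the visit wording in 7.1 is loose. Neither scale is scheduled at screening, and follow-up is a phone call, although 6.2.5 and 14.3 call it a visit. That is a reason to reconcile the sections rather than to leave them.

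**Conclusion.** The inconsistency is real and minor. Sections 3.5.2, 7.1 and 9.3.3 cannot all be read as written alongside 6.2.4, 6.2.5 and Section 18, because no TSRQ follows any participant's last session visit. The uncovered share is 25% of post-session windows with full completion and about 26% to 29% under the stated dropout limit, assuming that all six leave after one, two or three sessions.

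What is lost is a supplementary, t-PBM-specific open-ended report of delayed effects, not the side-effect data as a whole. With full completion and balanced orders the gap falls evenly on the doses. It could modestly affect the tolerability comparison if withdrawals cluster after one dose; the contrast of 55% with 77% to 80% is an outer illustration, not an expectation. The primary endpoint, sample size and significance level are unaffected.

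**What to change.** Add the TSRQ to the self-report list in 6.2.4 and mark it in the follow-up column of Section 18, so that 6.2.5 inherits it. Have it completed remotely in Acquire with the SAFTEE, and attribute the answers to the last dose received. State in 6.2.3 whether the TSRQ at experimental visits is completed before or after the scan, so that each answer can be assigned to a dose and a window.

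If the TSRQ is meant to cover at-session effects only, say so in 3.5.2 and 7.1 instead, and leave the schedule as it is.

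The first option costs one short form per participant at a contact that already takes place, plus a small protocol and eCRF change. It will not recover every withdrawal, since 6.2.5 can promise only an effort to reach people. The second option costs a wording change.
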